4.6 TREATMENT, PATIENT, AND STUDY DISCONTINUATION

Patients must permanently discontinue study treatment (Xofluza and oseltamivir) if they experience any of the following:

- Intolerable toxicity related to study treatment, including development of an immune-mediated adverse event determined by the investigator to be unacceptable given the individual patient's potential response to therapy and severity of the event
- Any medical condition that may jeopardize the patient's safety if he or she continues study treatment
- Investigator determines it is in the best interest of the patient
- Pregnancy
- Anaphylaxis or other severe hypersensitivity reaction
- Loss of clinical benefit as determined by the investigator after an integrated assessment of clinical status (e.g., symptomatic deterioration such as pain secondary to disease) (see Section 3.1.1 for details)

The primary reason for study treatment discontinuation should be documented in the patient's medical records. Patients who discontinue study treatment prematurely will be replaced.

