4.6.1 PATIENT DISCONTINUATION FROM STUDY

Patients have the right to voluntarily withdraw from the study at any time for any reason. In addition, the investigator has the right to withdraw a patient from the study at any time. Reasons for withdrawal from the study may include, but are not limited to, the following:

- Withdrawal of consent
- Study termination or site closure
- Patient non-compliance, defined as failure to comply with protocol requirements as determined by the Investigator

Every effort should be made to obtain information on patients who withdraw from the study. The primary reason for withdrawal from the study should be documented in the patient's medical records. If a patient requests to be withdrawn from the study, this request must be documented in the source documents and signed by the investigator. Patients who withdraw from the study may be replaced.

If a patient withdraws from the study, the study staff may use a public information source (e.g., county records) to obtain information about survival status.

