Each Party shall monitor and, as applicable, request feedback from the other Party regarding AE report timeliness in accordance with its own procedures. The Parties agree to provide written responses in a timely manner to inquiries from the other Party regarding AE reports received outside the agreed upon Agreement timelines. If there is any detection of trends of increasing or persistent non-compliance to transmission timelines stipulated in this Agreement, both Parties agree to conduct ad hoc or institute a regular joint meeting to address the issue.

In case of concerns related to non-compliance of processes, other than exchange timelines, with this Agreement, the Parties will jointly discuss and collaborate on clarifying and resolving the issues causing non-compliance. Every effort will be made by the non-compliant Party to solve the non-compliance issues and inform the other Party of the corrective and preventative actions taken.

Upon justified request, given sufficient notice of no less than sixty (60) calendar days, an audit under the provisions of this Agreement can be requested by either Party. The Parties will then discuss and agree in good faith upon the audit scope, agenda and execution of the audit. The requesting Party will bear the cost of the audit.

STATISTICAL CONSIDERATIONS

The study plans to enroll a total of 30 allogeneic bone marrow transplant patients who will be randomized at 1:1 to the two study arms. The primary endpoint data will be analyzed on the basis of a modified intention-to-treat (ITT) principle for patients with viral loads measurements at both the baseline and day 10.

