For secondary viral loads related endpoints, summary statistics in terms of mean, standard deviation, median and range will be calculated for each arm at each time points among patients with relevant measurements. Longitudinal analyses using mixed effects repeated measures will be used to model the mean viral loads overall time. Contrasts of interest including between arm differences will be explored using simultaneous tests of general linear hypotheses. If normality is a concern, log-transformed and standardized viral load data will be used. Longitudinal analysis will be carried out among patients with at least one relevant viral load measurement. Kaplan-Meier estimates will be generated for time to events endpoints such as time to Improvement of Individual Influenza Symptoms, the time to viral clearance and time to return to preinfluenza health status for each study arm. Between study arm difference in these endpoints will be explored using the generalized Wilcoxon test.

Categorical data such as the occurrence of treatment-emergent variants of neuraminidase and polymerase by direct next-generation sequencing and AE's will be summarized in terms of counts and proportions separately for each arm.

Between arm difference in the categorical variable will be explored using Fisher's exact test. The study is likely will not have adequate power to detect between arm differences and all the between arms comparisons are considered exploratory. Summary statistics generated for study endpoints for each arm will provide useful information for planning future studies.

The power calculations were performed using PASS 15 Power Analysis and Sample Size Software (2017). NCSS, LLC. Kaysville, Utah, USA, ncss.com/software/pass. All comparisons will be two-tailed, with a significance level at 0.05 and 95% confidence intervals will also be reported. All analyses will be performed in SAS Version 9.4 (2019), SAS Institute, Inc., Cary, NC; and R Version 4.0.4 (2021).

Note: The statistical considerations section was written by [name], MS, and revised by [name], in the Division of Biostatistics, Department of Population Health Sciences, Weill Cornell Medicine.

Influenza sequence analysis will be performed by [name], Director of Systems Genomics Section at the Laboratory of Parasitic Diseases of NIAID/NIH and expert in Influenza evolution.

No interim analysis is planned for this study

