6.2 STUDY MEDICAL MONITORING REQUIREMENTS

This clinical research study will be monitored both internally by the PI and externally by the Weill Cornell Medicine IRB. In terms of internal review, the PI will continuously monitor and tabulate AEs. Appropriate reporting to the Weill Cornell Medicine IRB will be made. The PI of this study will also continuously monitor the conduct, data, and safety of this study to ensure that:

- Interim analyses occur as scheduled,
- Stopping rules for toxicity and/or response are met,
- Risk/benefit ratio is not altered to the detriment of the subjects,
- Appropriate internal monitoring of AEs and outcomes is done,
- Over-accrual does not occur,
- Under-accrual is addressed with appropriate amendments or actions, and
- Data are being appropriately collected in a reasonably timely manner.

Routine monitoring will be carried out via a periodic team conference among investigators during which toxicity data, including all SAEs, will be reviewed and other issues relevant to the study such as interim assessment of accrual, outcome, and compliance with study guidelines, will be discussed. Monitoring will be carried out on an ongoing basis. The severity, relatedness, and whether or not the event is expected will be reviewed.

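### Randomised patients without a day-10 viral load drop out of both co-primary analyses for reasons that can depend on outcome, and the plan does not say that replaced patients stay in

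*Combined protocol and SAP*

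**What the plan says.** Section 4.6 lists the reasons for permanently stopping study treatment. They include intolerable toxicity and "Loss of clinical benefit as determined by the investigator after an integrated assessment of clinical status", with symptomatic deterioration as the example. It then states, with no exception by reason: "Patients who discontinue study treatment prematurely will be replaced". Section 4.6.1 deals separately with leaving the study: "Patients who withdraw from the study may be replaced".

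The Statistical Considerations (after section 5.4.12) plan 30 patients "who will be randomized at 1:1 to the two study arms". They analyse the primary endpoint on a "modified intention-to-treat (ITT) principle for patients with viral loads measurements at both the baseline and day 10". The first co-primary analysis is a paired test of the day-10 change within each arm. The second is the difference in change between arms.

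A wider set is used only for the secondary viral-load endpoints, which have a mixed-effects repeated-measures model: "Longitudinal analysis will be carried out among patients with at least one relevant viral load measurement".

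The plan has no rule for a missing day-10 value or a death before day 10, and no primary analysis of all randomised patients. It does not say whether a replaced patient stays in the analysis or how a replacement is allocated to an arm.

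**The concern.** Stopping, withdrawal, death and a missed day-10 visit all occur after randomisation, and each can be related to how the infection is going. A set defined by having a day-10 value is therefore partly selected on outcome. Filling the empty place with a new patient restores the number analysed but not the missing result.

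Two things are at stake. The first is the within-arm decline, which is co-primary. The plan also says that the per-arm summaries will inform later studies, so a decline that is too large would carry into the next design. The second is the between-arm difference, which is distorted if one arm loses more patients with high load than the other.

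**Working it through.** **Inputs from the documents.** 15 patients per arm; SD about 3 log10 at baseline and similar at day 10; detectable differences of 2.33 log10 within an arm and 1.1 SD between arms, each at 80% power and two-sided 0.05 (Statistical Considerations). Table 4 in section 1.3, for the add-on trial in hospitalised patients: withdrawal from treatment due to AE 1.3% with baloxavir and 3.2% with placebo; deaths 1.7% and 5.6%.

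**Step 1: the plan's own figures.**
- Paired t-test, n = 15, SD of the change 3: noncentrality 2.33/3 × √15 = 3.01, power 79.9%. The plan's figure reproduces. With both SDs equal to 3, an SD of the change of 3 implies a baseline/day-10 correlation of 0.5, because 3 × √(2 × (1 − 0.5)) = 3. The plan does not state this correlation; it is implied.
- Two-sample t-test, 15 per arm, 1.1 SD: noncentrality 1.1 × √(15/2) = 3.01, power 82.8%. This is consistent with the stated 80%.

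**Step 2: number analysed.** If lost patients are not made up, power within arm and between arms is 76.6% and 80.0% at 14 per arm, 73.0% and 76.8% at 13, and 68.8% and 73.1% at 12. Replacement recovers this power and does nothing for selection.

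**Step 3: worst-case shift in one arm.** Assume that the k patients with the highest day-10 loads out of 15 are the ones lost. The expected three largest of 15 standard normal values are 1.736, 1.248 and 0.948. The mean of the remaining day-10 values moves down by 3 × (sum of the k largest)/(15 − k). The regression slope of change on day-10 load is (9 − 0.5 × 9)/9 = 0.5, so half of that shift reaches the mean change.

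| k lost of 15 | Shift in day-10 mean | Shift in mean change |
|---|---|---|
| 1 | 3 × 1.736/14 = 0.37 | -0.19 |
| 2 | 3 × 2.984/13 = 0.69 | -0.34 |
| 3 | 3 × 3.932/12 = 0.98 | -0.49 |

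If loss followed the change itself rather than day-10 load, the slope would be 1 and the shift in mean change would be 0.37, 0.69 or 0.98. That is more extreme still.

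**Step 4: equal loss.** If both arms lose the same number in the same way, the shifts cancel in the between-arm difference. They do not cancel within an arm: losing 2 of 15 makes each decline look 0.34 log10 larger than it is.

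**Step 5: unequal loss at the only rates the documents give.** With the top fraction p lost, the mean change shifts by 0.5 × 3 × φ(z)/(1 − p), where z is the upper-p normal quantile and φ the normal density.
- AE withdrawals: 1.3% gives 0.051 and 3.2% gives 0.111. The difference is 0.06 log10.
- Deaths added, taking the two as non-overlapping: 1.3 + 1.7 = 3.0% gives 0.105 and 3.2 + 5.6 = 8.8% gives 0.263. The difference is 0.16 log10.
- Half-width of the 95% confidence interval for the between-arm difference: 2.048 × 3 × √(2/15) = 2.24 log10.

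The bias is therefore 0.06/2.24 = 3% to 0.16/2.24 = 7% of the half-width. At these rates placebo loses more, so the control arm is flattered and the bias works against baloxavir. Greater loss in the baloxavir arm would reverse it.

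**The case against.** The strongest case against runs as follows. Stopping treatment (section 4.6) is not leaving the study (section 4.6.1). Appendix 1 schedules the day-10 swab without tying it to continued treatment, section 4.6.1 asks for every effort to obtain information on those who withdraw, and section 4.5.8 allows samples taken before withdrawal to be analysed. The secondary endpoints already include the day-10 between-arm difference, analysed by a model that admits patients with at least one measurement. The trial is a pilot and calls its between-arm comparisons exploratory. Perfect selection on day-10 load is unrealistic, since several listed reasons for stopping, such as pregnancy or anaphylaxis, need not track load.

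Much of this stands, and it rules out some stronger readings that a reader might infer:
- **That every replaced patient is deleted from the analysis.** No section says so. A patient who stops treatment but gives a day-10 swab meets the primary-set definition. Loss is certain only when there is no day-10 value; for the rest the plan is silent.
- **That replacement breaks the monitoring item "Over-accrual does not occur".** That item defines no limit, section 4.1 says approximately 30 patients, and a replacement that the protocol itself provides for is not shown to be over-accrual.
- **That the modified ITT label is contradicted.** The Statistical Considerations state the modification openly.
- **That the between-arm result is badly biased, or biased towards baloxavir.** Neither the size nor the direction can be derived from the documents.

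The objection does not dispose of the point. The model using all available data is reserved for secondary endpoints, the exploratory label covers only between-arm comparisons, and the within-arm change is co-primary.

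**Conclusion.** The concern holds in this form: the primary set drops randomised patients who lack a day-10 value, for reasons that can depend on outcome, and the plan leaves open whether replaced patients who have a day-10 value are kept. The within-arm decline can be overstated even with equal loss. The between-arm difference is biased in either direction if loss differs by arm.

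The shifts of -0.19, -0.34 and -0.49 log10 are an upper illustration, resting on normal loads, SD 3, correlation 0.5 and loss tied perfectly to day-10 load. The documents give no stopping rate for this population. The Table 4 rates come from hospitalised patients and count only AE withdrawals and deaths. At those rates the between-arm bias is small beside the confidence interval, even with worst-case selection. The change is still worth making, because a better analysis is already in the plan and moving it to the primary endpoint costs little.

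**What to change.** - State in sections 4.6 and 4.6.1 that replacements are additions, that no randomised patient is removed from the analysis, and how replacements are allocated.
- State that scheduled swabs through day 10 continue after study treatment stops.
- Run the primary day-10 comparison with the repeated-measures model already planned for the secondary endpoints, in all randomised patients with a baseline value. Take the within-arm day-10 changes from the same model. Keep the set "for patients with viral loads measurements at both the baseline and day 10" as a sensitivity analysis.
- State how deaths before day 10 are handled, since the model would otherwise treat them as ordinary missing values.
- Confirm that RNA is quantified at days 4 and 7, as the secondary endpoints and the model need. Section 4.2.1 mentions only the pre-treatment and last post-treatment swabs.

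The cost is mainly protocol wording, with no new sample size. With 15 per arm analysed, the plan's tests keep 79.9% and 82.8% power. There are two downsides: fewer complete treatment courses among the analysed patients, and reliance on a missing-at-random assumption, which the completer analysis and the rule for deaths should accompany.

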4.6.1 PATIENT DISCONTINUATION FROM STUDY

Patients have the right to voluntarily withdraw from the study at any time for any reason. In addition, the investigator has the right to withdraw a patient from the study at any time. Reasons for withdrawal from the study may include, but are not limited to, the following:

- Withdrawal of consent
- Study termination or site closure
- Patient non-compliance, defined as failure to comply with protocol requirements as determined by the Investigator

Every effort should be made to obtain information on patients who withdraw from the study. The primary reason for withdrawal from the study should be documented in the patient's medical records. If a patient requests to be withdrawn from the study, this request must be documented in the source documents and signed by the investigator. Patients who withdraw from the study may be replaced.

If a patient withdraws from the study, the study staff may use a public information source (e.g., county records) to obtain information about survival status.

4.6.2 STUDY DISCONTINUATION

The investigator has the right to terminate this study at any time. Reasons for terminating the study may include, but not limited to, the following:

- The incidence or severity of adverse events in this or other studies indicates a potential health hazard to patients
- Patient enrollment is unsatisfactory

5. ASSESSMENT OF SAFETY

5.1 SPECIFICATION OF SAFETY VARIABLES

Safety assessments will consist of monitoring and reporting adverse events (AEs) and serious adverse events (SAEs) per protocol. This includes all events of death, and any study specific issue of concern.

5.2 ADVERSE EVENTS

An AE is any unfavorable and unintended sign, symptom, or disease temporally associated with the use of an investigational medicinal product (IMP) or other protocol-imposed intervention, regardless of attribution. This includes the following:

- AEs not previously observed in the subject that emerge during the protocol-specified AE reporting period, including signs or symptoms associated with SCT patients with influenza that were not present prior to the AE reporting period.
- Preexisting medical conditions (other than the condition being studied) judged by the investigator to have worsened in severity or frequency or changed in character during the protocol-specified AE reporting period.

5.3 SERIOUS ADVERSE EVENTS

An AE should be classified as an SAE if the following criteria are met:

- It results in death (i.e., the AE actually causes or leads to death).
- It is life threatening (i.e., the AE, in the view of the investigator, places the subject at immediate risk of death. It does not include an AE that, had it occurred in a more severe form, might have caused death.).
- It requires or prolongs inpatient hospitalization.
- It results in persistent or significant disability/incapacity (i.e., the AE results in substantial disruption of the subject's ability to conduct normal life functions).
- It is considered a significant medical event by the investigator based on medical judgment (e.g., may jeopardize the subject or may require medical/surgical intervention to prevent one of the outcomes listed above).

5.3.1 METHODS AND TIMING FOR ASSESSING AND RECORDING SAFETY VARIABLES

The investigator is responsible for ensuring that all AEs and SAEs that are observed or reported during the study are collected and reported to the FDA, appropriate IRB(s), and Genentech, Inc. in accordance with CFR 312.32 (IND Safety Reports)

5.3.2 ADVERSE EVENT REPORTING PERIOD

The study period during which AEs and SAEs as described in **section J** where the patient has been exposed to Genentech product must be reported. Reporting period begins after informed consent is obtained and initiation of study treatment and ends 30 days following the first administration of study treatment or study discontinuation/termination, whichever is earlier. After this period, investigators should only report SAEs that are attributed to prior study treatment.

5.3.3 ASSESSMENT OF ADVERSE EVENTS

All AEs and SAEs whether volunteered by the subject, discovered by study personnel during questioning, or detected through physical examination, laboratory test, or other means will be reported appropriately. Each reported AE or SAE will be described by its duration (i.e., start and end dates), regulatory seriousness criteria if applicable, suspected relationship to the baloxavir combination therapy (see following guidance), and actions taken.

To ensure consistency of AE and SAE causality assessments, investigators should apply the following general guideline:

YES

There is a plausible temporal relationship between the onset of the AE and administration of the baloxavir combination therapy and the AE cannot be readily explained by the subject's clinical state, intercurrent illness, or concomitant therapies; and/or the AE follows a known pattern of response to the baloxavir combination therapy or with similar treatments; and/or the AE abates or resolves upon discontinuation of the baloxavir combination therapy or dose reduction and, if applicable, reappears upon re- challenge.

NO

Evidence exists that the AE has an etiology other than the baloxavir combination therapy (e.g., preexisting medical condition, underlying disease, intercurrent illness, or concomitant medication); and/or the AE has no plausible temporal relationship to baloxavir combination therapy administration (e.g., cancer diagnosed 2 days after first dose of study drug).

Expected adverse events are those adverse events that are listed or characterized in the Package Insert (P.I) or current Investigator Brochure (I.B).

Unexpected adverse events are those not listed in the P.I or current I.B or not identified. This includes adverse events for which the specificity or severity is not consistent with the description in the P.I. or I.B. For example, under this definition, hepatic necrosis would be unexpected if the P.I. or I.B. only referred to elevated hepatic enzymes or hepatitis.

For patients receiving combination therapy, causality will be assessed individually for each protocol-mandated therapy.

5.3.4 Management Criteria for Abnormal Liver Function Tests and Data and Safety Monitoring Plan (DSMP)

Management Criteria for Abnormal Liver Function tests have been designed to ensure patient safety and evaluate liver event etiology (see Guidance for Industry Drug-Induced Liver Injury: Premarketing Clinical Evaluation, FDA: 2009; available from: <https://www.fda.gov/downloads/Guidances/UCM174090.pdf>).

The Weill Cornell Medicine DSMB will be used for this investigator-initiated study. The following information will be submitted to the WCM DSMB:

Laboratory results

- Blood hematology and chemistry
- Blood liver chemistry

Adverse Events and Stopping Rules

The following adverse events will be submitted to the WCM DSMB and may cause the subject to terminate protocol treatment, **at the discretion of the PI**:

1. AST or ALT $> 5 \times$ upper limit of normal (ULN)
2. AST or ALT $> 3 \times$ ULN and total bilirubin (TBL) $> 2 \times$ ULN or INR > 1.5 , if INR is measured
3. Severe drug reaction, including rash or fever (as determined by the PI)
4. AST or ALT $> 3 \times$ ULN with signs or symptoms compatible with hepatitis or hypersensitivity (e.g., fatigue, nausea, vomiting, right upper quadrant pain or tenderness, jaundice, fever, rash, eosinophilia [$> 5\%$])

Action to be Taken by Investigator

If any abnormal liver chemistry criterion is met, the investigator or sub investigator must do the following:

- consider discontinuation only if transaminase elevation is not otherwise explained
- Following the initial observed elevation, every effort should be made to have the patient return to the clinic within 72 hours (if already discharged from hospital) to repeat liver function chemistries and for further hepatic evaluation.
- Every effort should be made to have the patients monitored 2 to 3 times per week until liver function chemistries (i.e., ALT, AST, ALP, TBL) resolve, stabilize per investigator judgement, or return to within the normal range or to baseline levels.
- Consultation with a specialist, such as a hepatologist, and liver imaging (i.e., ultrasound, magnetic resonance imaging [MRI], computerized tomography) should be considered for worsening laboratory values or symptoms.

WCM IRB policies will be followed for this study, including the Immediate Report Policy. Any SAEs will be reported to the IRB following these policies, and will also be reported to the funding source (Genentech Inc.) within 30 days of the study team learning of the SAE. The WCM DSMB comments/review will be submitted to the IRB at the time of continuing review and submitted to the funding source (Genentech, Inc.) at the time of each WCM DSMB completion.

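### The protocol's list of what is submitted to the DSMB does not include deaths or serious adverse events as a class

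*Combined protocol and SAP*

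**What the plan says.** Section 5.3.4 of the combined protocol and SAP (liver-test management and the data and safety monitoring plan) states that "The Weill Cornell Medicine DSMB will be used for this investigator-initiated study". It then opens a list with "The following information will be submitted to the WCM DSMB". The laboratory items are "Blood hematology and chemistry" and "Blood liver chemistry". Under a subheading on adverse events and stopping rules it continues: "The following adverse events will be submitted to the WCM DSMB and may cause the subject to terminate protocol treatment", at the PI's discretion. Four items follow: three defined by ALT or AST thresholds, alone or with bilirubin, INR or symptoms, and one for a severe drug reaction as determined by the PI.

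The end of the same section gives the SAE route: "Any SAEs will be reported to the IRB following these policies, and will also be reported to the funding source". The DSMB appears next only as the source of comments that are passed to the IRB and the funder.

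Three other sections bear on the point:

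- Section 5.3.1 has all AEs and SAEs reported to the FDA, the IRB(s) and Genentech.
- Section 5.4.2.2 requires every death in the reporting period to be reported, whatever its cause, but does not say to whom.
- Section 6.2 says the study is "monitored both internally by the PI and externally by the Weill Cornell Medicine IRB". It has all SAEs reviewed at a periodic conference of the investigators and does not mention the DSMB.

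**The concern.** A safety board is of most use for events that are serious and hard to attribute in a single case. Here the board is sent liver enzymes and blood counts. The text gives no route by which it would learn of a death from respiratory failure, a serious infection or an ICU admission, unless the event also met a liver criterion or the PI judged it a severe drug reaction.

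The population makes this matter. Section 1.3 describes more lower-respiratory progression and increased death from influenza in stem cell transplant recipients, and says that no randomized trial of baloxavir in immunocompromised patients is available. The PI's judgment is also the filter for the one listed item that is not a liver criterion, so an event attributed to influenza or to the underlying disease would not pass it.

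**Working it through.** No figure in the plan is at issue, so the check has two parts: tracing who is sent what, and gauging how often the gap would be met.

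**Routes, side by side**

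| Information | Where stated | Recipients named | DSMB named? |
|---|---|---|---|
| Hematology, chemistry, liver chemistry | 5.3.4 | DSMB | Yes |
| Three liver-enzyme criteria; severe drug reaction | 5.3.4 | DSMB | Yes |
| SAEs | 5.3.4 (end) | IRB, Genentech | No |
| All AEs and SAEs | 5.3.1 | FDA, IRB(s), Genentech | No |
| SAEs, special-interest events, pregnancy | 5.4.8 | Genentech | No |
| Deaths | 5.4.2.2 | Not specified | No |
| Review of all SAEs | 6.2 | Investigators' conference | No |
| External monitoring | 6.2 | IRB | No |

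No section names the DSMB as a recipient of deaths or of SAEs as a class, and no section says they are withheld from it. An independent data monitoring committee appears in the abbreviation list but is given no task.

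**How often the gap would be met**

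Inputs: 30 patients randomized 1:1 (Section 3.1), so 15 per arm; the FLAGSTONE table in Section 1.3. SAEs: 29/239 = 12.13% on baloxavir plus NAI, 19/124 = 15.32% on placebo plus NAI. Deaths: 4/239 = 1.67% and 7/124 = 5.65%.

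Expected patients = 15·p₁ + 15·p₂; P(at least one) = 1 − (1 − p₁)¹⁵(1 − p₂)¹⁵.

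- SAEs: 1.82 + 2.30 = 4.12 patients; P = 1 − 0.1437 × 0.0825 = 0.99.
- Deaths: 0.25 + 0.85 = 1.10; P = 1 − 0.7763 × 0.4183 = 0.68.

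Using the pooled death rate instead, 11/363 = 3.03%, gives 30 × 0.0303 = 0.91 deaths and 1 − 0.9697³⁰ = 0.60. The arm-specific calculation suits this trial better, because FLAGSTONE's arms were roughly 2:1 and these are 1:1.

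FLAGSTONE enrolled hospitalized patients, while this trial takes immunocompromised inpatients and outpatients, so the transfer of rates is an assumption. Halving and doubling both arms' rates shows the range:

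| Rates assumed | Patients with an SAE | Deaths | P(at least one death) |
|---|---|---|---|
| Half FLAGSTONE | 2.06 | 0.55 | 0.43 |
| FLAGSTONE | 4.12 | 1.10 | 0.68 |
| Twice FLAGSTONE | 8.24 | 2.20 | 0.90 |

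Some of these SAEs might meet a listed item and so reach the board; the documents do not allow that share to be estimated.

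**The case against.** The best case for the plan has four parts.

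- **The list is not declared exclusive.** The event items sit in a section on liver tests and concern individual treatment termination, so they may not be the board's whole remit. The unnamed recipients of death reports could include the DSMB, and the institutional board may have submission rules of its own that are not in these documents. This stands against anyone inferring that deaths and SAEs never reach the board. It does not remove the gap: the protocol provides no such route, and the SAE paragraph mentions the DSMB without making it a recipient.
- **Others outside the team do see SAEs.** The IRB receives them under its immediate-report policy, the FDA receives them under Section 5.3.1, and Section 5.4.10 adds expedited and six-monthly reporting. This stands. A reader might infer that nobody independent sees these events, and the documents contradict that. These routes are not the DSMB's review, however.
- **With 15 per arm the board could detect little by comparison.** From zero in one arm, 5 versus 0 deaths is the smallest split with a two-sided Fisher p below 0.05 (p = 0.042; 4 versus 0 gives 0.10). With about one death expected, the benefit lies in case review, not in testing an imbalance. This also stands.
- **Comparison by arm is a separate matter.** Section 5.3.4 does not say that even the listed items are shown by arm, so adding SAEs would not supply that.

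**Conclusion.** The concern holds in this form: the protocol does not provide for deaths, or for SAEs outside the liver and severe-drug-reaction items, to be submitted to the only safety board that it gives a role. This is more than silence, because there is a specific list and these events are not on it.

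On FLAGSTONE rates the gap would concern about 4 patients with an SAE and 1.1 deaths, with a 68% chance of at least one death (43% to 90% if the rates are halved or doubled). These figures show that the situation is likely to arise. They do not predict rates in this population.

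Two further readings are not supported. A reader might take the board's laboratory data to be liver values only, but full hematology and chemistry are listed. A reader might also call this the first human study of the combination, since Section 1.3 says no human combination data exist. The FLAGSTONE table in the same section reports 239 patients on baloxavir plus an NAI.

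**What to change.** - In Section 5.3.4, add all deaths and all SAEs to the list of information submitted to the DSMB.
- In the SAE paragraph of Section 5.3.4 and in Section 5.4.2.2, name the DSMB as a recipient, and in the latter state who the other recipients of death reports are.
- In Section 6.2, name the DSMB alongside the IRB as external monitor, so that it agrees with Section 5.3.4.

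Separate lines for ICU admission, ventilation or pneumonia are not needed, since such events would normally qualify as SAEs under Section 5.3. A count by coded arm for the DSMB is an optional addition. It would need someone outside the blinded team to prepare it, and the documents assign that task to no one.

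The cost is protocol wording and minor added reporting work. The board is already designated and the events are already collected. No dose, treatment rule or analysis changes.
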